#### **2.8.1.1 Adverse events of special interest / grouping of AEs**

An adverse event of special interest is a grouping of adverse events that are of scientific and medical concern specific to compound eltrombopag. These groupings are defined using

MedDRA terms, SMQs (standardized MedDRA queries), HGLTs (high level group terms), HLT (high level terms) and PTs (preferred terms). Customized SMQs (Novartis MedDRA queries, NMQ) may also be used. A NMQ is a customized group of search terms which defines a medical concept for which there is no official SMQ available or the available SMQ does not completely fit the need. It may include a combination of single terms and/or an existing SMQ, narrow or broad.

At the project level, a sas dataset named eCRS contains the exact composition of the adverse events groupings will be used to map reported adverse events to the notable adverse events groupings. This dataset may be updated (i.e., it is a living document) based on review of accumulating trial data, and it is the most up to date version at the time of DB lock that will be used. Note that certain adverse events may be reported within multiple groupings.

For each specified AESI, number and percentage of patients with at least one event of the AESI occurring during on treatment period will be summarized. Summaries of these AESIs will be provided by subgroup (see [Section 2.2.1](#)). A listing of all grouping levels down to the MedDRA preferred terms used to define each AESI will be generated.

## **2.8.2 Deaths**

The number and percentage of deaths occurring during the on-treatment period and at any time during the study will be provided. Deaths occurring during the on-treatment period will be further summarized by system organ class and preferred term. All deaths will be listed and flagged appropriately.

## **2.8.3 Laboratory data**

On analyzing laboratory data, data from all sources (central and local laboratories) will be combined. The summaries will include all assessments available for the lab parameter collected no later than 30 days after the last study treatment administration date (see [Section 2.1.1](#)).

Grading of laboratory values will be assigned programmatically as per NCI Common Terminology Criteria for Adverse Events (CTCAE), version 4.03. The calculation of CTCAE grades will be based on the observed laboratory values only, clinical assessments will not be taken into account.

CTCAE Grade 0 will be assigned for all non-missing values not graded as 1 or higher. Grade 5 will not be used.

## **Hematology and clinical chemistry laboratory parameters**

The following summaries will be produced for hematology and clinical chemistry laboratory data (by laboratory parameter):

- Worst post-baseline CTC grade (regardless of the baseline status). Each subject will be counted only for the worst grade observed post-baseline.
- Shift tables using CTC grades to compare baseline to the worst on-treatment value
- For laboratory tests where CTC grades are not defined, shift tables using the low/normal/high/(low and high) classification to compare baseline to the worst on-treatment value.

- Trends of lab parameter values over time (baseline and selected on-treatment timepoints) should be displayed via boxplots based on time windows and corresponding tables displaying the statistics used for the box plots by the selected time points and the selected lab parameters.

The following listings will be produced for the laboratory data:

- Listings of all laboratory data by subject and visit/time, with CTC grades and classification relative to the laboratory normal range. Lab data collected during the post-treatment period will be flagged.
- Listing of all CTC grade 3 or 4 laboratory toxicities by subject and visit/time

In addition, regardless of the transfusion or G-CSF, laboratory tests (Platelet counts, Hemoglobin, Neutrophil count) value and change from baseline will be listed and summarized in scheduled visits using descriptive statistics (mean, SD, median, interquartile range, and range).

### **Coagulation**

Coagulation assays data (Prothrombin time, international normal ratio, Activated partial thromboplastin time) will be listed.

### **Liver function parameters**

Liver function parameters of interest are Total bilirubin (TBIL) and Direct bilirubin (DBIL), ALT, AST and alkaline phosphatase (ALP). The number (%) of patients with worst post-baseline values as per Novartis Liver Toxicity guidelines will be summarized.

For summaries based on multiple parameters, the results must be obtained from samples collected within maximum 30 days of each other.

The following summaries will be produced:

- ALT or AST > 3xULN and (TBIL or DBIL > 2xULN) and (ALP < 2xULN or missing)
- ALT or AST > 3xULN and (TBIL or DBIL > 2xULN)
- ALT or AST > 3xULN and (TBIL or DBIL > 1.5xULN)
- ALT or AST > 20xULN
- ALT or AST > 10xULN
- ALT or AST > 5xULN
- ALT or AST > 3xULN
- ALT > 20xULN
- ALT > 10xULN
- ALT > 5xULN
- ALT > 3xULN
- AST > 20xULN

- AST > 10xULN
- AST > 5xULN
- AST > 3xULN
  
- DBIL > 2xULN
- DBIL > 1.5xULN
- TBIL > 2xULN
- TBIL > 1.5xULN
  
- ALP > 1.5xULN

## **2.8.4 Other safety data**

### **2.8.4.1 ECG**

A standard 12 lead ECG will be performed:

- at screening or baseline (Triplicate ECG to be collected to assess QTcF intervals)
- at Week 13, Week 26 and Week 52 (in the extension part ECG is only for the responders)
- at the end of treatment

### **Data handling**

In case the study requires ECG replicates at any assessment, the average of the ECG parameters at that assessment should be used in the analyses.

### **Data analysis**

The following summaries will be produced for ECG results:

- Descriptive statistics including mean, SD, median, 25th and 75th percentiles, minimum, and maximum will be summarized for ECG values at each visit.
- The number and percentage of subjects with notable ECG values below at each visit will be presented.
  - QT, QTcF
    - New value of > 450 and  $\leq$  480 ms
    - New value of > 480 and  $\leq$  500 ms
    - New value of > 500 ms
    - Increase from Baseline of > 30 ms to  $\leq$  60ms
    - Increase from Baseline of > 60 ms
  - HR
    - Increase from baseline >25% and to a value > 100 bpm
    - Decrease from baseline >25% and to a value < 50 bpm
  - PR

- Increase from baseline >25% and to a value > 200 ms
- New value of > 200 ms
- QRS
  - Increase from baseline >25% and to a value > 120 ms
  - New values of QRS > 120 ms

A listing of all ECG assessments will be produced and notable values will be flagged. In the listing, the assessments collected during the post-treatment period will be flagged.

#### 2.8.4.2 Vital signs

Vital sign assessments are performed in order to characterize basic body function. The following parameters were collected: height (cm), weight (kg), body temperature (°C), pulse rate, systolic and diastolic blood pressure (mmHg).

#### Data handling

Vital signs collected on treatment will be summarized. Values measured outside of on treatment period will be flagged in the listings.

#### Data analysis

For analysis of vital signs the clinically notable vital sign criteria are provided in [Table 2-2](#) below.

**Table 2-2 Clinically notable changes in vital signs**

Vital sign (unit)	Clinically notable criteria	
	above normal value	below normal value
Weight (kg)	increase > 10% from baseline	decrease > 10% from baseline
Systolic blood pressure (mmHg)	>=180 with increase from baseline of >=20	<=90 with decrease from baseline of >=20
Diastolic blood pressure (mmHg)	>=105 with increase from baseline of >=15	<=50 with decrease from baseline of >=15
Pulse rate (bpm)	>=100 with increase from baseline of >25%	<=50 with decrease from baseline of > 25%
Body temperature (°C)	>= 39.1	-

The number and percentage of subjects with notable vital sign values (high/low) will be presented.

In addition, values and change from baseline of vital signs will be summarized at each visit by descriptive statistics including mean, SD, median, 25th and 75th percentiles, minimum, and maximum.

A listing of all vital sign assessments will be produced and notable values will be flagged. In the listing, the assessments collected outside of on-treatment period will be flagged.

#### **2.8.4.3 Bone Marrow Examination**

Following bone marrow examination data will be listed.

- Bone marrow aspiration
- Bone marrow biopsy
- Chromosomal test (Karyotype and FISH)
- Peripheral blood smear test

#### **2.9 Pharmacokinetic endpoints**

Not applicable for final analysis.

NA.

#### **2.10 PD and PK/PD analyses**

Not applicable for final analysis.

#### **2.11 Cytogenetic abnormalities and clonal evolution**

##### **Cytogenetic abnormalities and clonal evolution observed during the study**

Cytogenetic abnormalities and clonal evolution will be selected from AE page in eCRF, and will be chosen as AE Preferred term = “clonal evolution / cytogenetic abnormality / AML / MDS / PNH”.

Clonal cytogenetic evolution will be evaluated during the study, and the rate of the subjects who developed any clonal evolution (e.g., clonal evolution to PNH, evolution to AML or MDS etc.) will be calculated in a summary table. Short narratives and relevant information for subjects with new cytogenetic abnormalities on study will be listed.

##### **GPI negative neutrophil level**

Shift tables using GPI negative neutrophil and RBC level ( $\leq 50\%$  and  $> 50\%$ ) to compare baseline to the worst on-treatment will be presented.

#### **2.12 Other Exploratory analyses**

Not Applicable.

#### **2.13 Interim analysis**

No formal interim analysis is planned for this trial. The primary analysis will be performed after all subjects have completed Week 26 or discontinued prior to Week 26. A final analysis will be performed after all subjects have completed the study. No formal testing of the primary endpoint will be performed in this study.

### 3 Sample size calculation

As this is a bridging study to support registration, an estimation strategy rather than formal hypothesis testing will be pursued. Approximately 36 subjects will be enrolled into the study based on the feasibility rather than statistical considerations. This number of subjects is considered appropriate to assess the efficacy and safety of eltrombopag in Asian patients.

#### 3.1 Primary analysis

Based on the Day 120 report in the pivotal study of CETB115AUS01T, the complete hematological response rate at Month 6 in Cohort 3+Extension is 43.7%. If the CR rate obtained in naive Asian patients with SAA treated with eltrombopag is expected to be 44.0%, a total of 36 subjects will result in a 95% CI lower bound of about 28%.

Below table shows the exact 95% CIs for various observed complete hematological response rate. The maximum half-width of the 95% CIs is 17.1%.

**Table 3-1 95% CIs for various observed response rate**

Total sample size	# of responders	Complete hematologic response rate (%)	95% CI (%)
36	14	38.9	(23.1, 56.5)
36	16	44.4	(27.9, 61.9)
36	18	50.0	(32.9, 67.1)

The 12 evaluable subjects for intensive PK sampling was chosen based on feasibility and practical considerationzs to assist in characterizing the PK of eltrombopag in Chinese subjects.

#### 3.2 Power for analysis of key secondary variables

Not Applicable

### 4 Change to protocol specified analyses

Below-listed endpoints were added to further support efficacy analysis beyond protocol.

- Maximum duration of Platelet and RBC transfusion free
- Proportion of subjects with transfusion decrease
- Changes in platelet count, hemoglobin and neutrophil count

### 5 Appendix

#### 5.1 Imputation rules

##### 5.1.1 Study drug

The following rule should be used for the imputation of the dose end date for a given study treatment component:

**Scenario 1:** If the dose end date is completely missing and there is no EOT page and no death date, the patient is considered as on-going:

The patient should be treated as on-going and the cut-off date should be used as the dose end date.

**Scenario 2:** If the dose end date is completely or partially missing and the EOT page is available:

Case 1: The dose end date is completely missing, and the EOT completion date is complete, then this latter date should be used.

Case 2: Only Year(yyyy) of the dose end date is available and yyyy < the year of EOT date:

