6.1.5 Treatment duration

The core treatment part of this study is 6 month from the start of eltrombopag treatment (Day 1 to Week 26). Participants assessed as responders at Week 26 will be eligible to enter the extension part and may continue treatment with eltrombopag and CsA after Week 26 until Week 52.

Core treatment part

The planned duration of eltrombopag treatment is 6 months in the core treatment part. Participants may be discontinued from treatment earlier due to unacceptable toxicity, disease progression and/or treatment is discontinued at discretion of the investigator or of the participant (see [Section 9.1.1](#)).

The administration of r-ATG will be from Day 1 to Day 5.

For all participants, CsA will be administered at doses that obtain the target trough level range for 6 months if well tolerated. CsA dose may be interrupted temporarily when clinically indicated at the discretion of the investigator or treating physician. The parenteral route of administration may be used temporarily for CsA administration if indicated. Temporary interruptions for transient toxicities or dose adjustments will be reported. Per protocol interruptions will not be reported as deviations.

Extension part

The participants assessed as responders at Week 26 are eligible to enter the extension part. Eltrombopag will be provided up to Week 52 for the participants who enter the extension part and are considered to require continued treatment. For the participants who meet the discontinuation criteria in [Section 9.1.1](#), the study treatment will be discontinued.

In extension part, CsA will last for at least 18 months after Week 26 if well tolerated (total duration is from Day 1 to at least Year 2). CsA will be maintained or tapered based on the discretion of the investigator according to local practice. It is recommended that CsA treatment dose last for at least 3 months after achieving the best hematologic response, and after that CsA is recommended to be tapered by 0.3 mg/kg every month or 1 mg/kg every 3 months. CsA dose may be decreased or interrupted temporarily when clinically indicated at the discretion of the investigator or treating physician. Temporary interruptions for transient toxicities or dose adjustments will be reported. Per protocol interruptions will not be reported as deviations. After Year 2 (Week 104), CsA administration will be at the discretion of the investigator, and will not be provided within the trial anymore.

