9.2 Study completion and post-study treatment

Study completion is defined as when the last participant finishes her/his Study Completion visit, and any repeat assessments associated with this visit have been documented and followed-up appropriately by the Investigator, or in the event of an early study termination decision, the date of that decision.

All treated participants should have a safety follow-up visit conducted 30 days after last administration of eltrombopag. The information collected is kept as source documentation. All SAEs reported during this time period must be reported as described in [Section 10.1.3](#). Documentation of attempts to contact the participant should be recorded in the source documentation.

The primary analysis will be performed after all participants have completed Week 26 or discontinued prior to Week 26. The primary analysis data will be summarized in the primary clinical study report (CSR). Following the cut-off date for the analysis reported in the primary CSR, the study will remain open. Ongoing participants will continue to receive study treatment and be followed as per the schedule of assessments, as long as participants derive benefit from eltrombopag.

The end of study defined as the earliest occurrence of one of the following:

1. All participants have died or discontinued from the study or complete the study participation per protocol.
2. Another clinical study becomes available that can continue to provide eltrombopag in this participant population and all participants ongoing are eligible to be transferred to that clinical study.

At the end of Year 2 in this study, participants who in the opinion of the Investigator are still deriving clinical benefit from further CsA treatment should be directed by the treating physician to receive the product through commercial channels locally. The final analysis will occur at the end of the study. All available data from all participants up to this cut-off date will be analyzed and summarized in a final CSR.

10 Safety monitoring and reporting

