**Figure 1-1 Study design**

Eligible subjects will be enrolled into the study and will receive eltrombopag (from Day 1 to Week 26) concomitantly with r-ATG (on Days 1-5) and CsA (from Day 1 to Week 26) in the core treatment part.

Efficacy assessments will be performed at Week 13 and Week 26 in the core treatment part of the study.

Participants who are assessed as responders (meeting CR or PR criteria) at Week 26 are eligible to the extension part of the study and continue treatment with eltrombopag and CsA after Week 26.

Study treatment should be discontinued if the participant is not assessed as a responder at Week 26.

During the extension part, eltrombopag treatment will be provided up to Week 52. CsA will be maintained or tapered at the investigator's discretion according to local practice, with a total duration of at least 2 years (18 months after Week 26).

End of treatment assessments will be performed after eltrombopag discontinuation anytime during the study. After that, safety follow-up visit will be performed 30 days after the discontinuation of eltrombopag, and participants will enter the long-term follow-up part, with yearly efficacy and clonal evolution assessments up to Year 3 (Week 156).

For non-responders at Week 26, and participants who relapse or receive alternative SAA treatment, safety follow-up visit will be performed 30 days after the discontinuation of eltrombopag, and then clonal evolution and survival will continue to be followed up to Year 3 (Week 156).

Participants who prematurely discontinue eltrombopag will have efficacy assessments at defined time points (Week 13, Week 26, Week 52 and yearly after), unless or until the occurrence of no response at Week 26, relapse or alternative SAA treatment (whichever comes first). Survival and clonal evolution data will be collected for all participants up to Year 3 (Week 156).

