#### Data included in the analysis

The analysis cutoff date for the final analysis of study data will be established at the end of the study.

All statistical analyses will be performed using all data collected in the database up to the data cutoff date. All data with an assessment date or event start date (e.g. vital sign assessment date or start date of an adverse event) prior to or on the cut-off date will be included in the analysis. Any data collected beyond the cut-off date will not be included in the analysis and will not be used for any derivations.

All events with start date before or on the cut-off date and end date after the cut-off date will be reported as 'ongoing'. The same rule will be applied to events starting before or on the cut-off date and not having documented end date. This approach applies, in particular, to adverse event, concomitant medication reports and exposure to eltrombopag. For these events, the end date will not be imputed and therefore will not appear in the listings.

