## **On-treatment assessment/event and observation periods**

For adverse event reporting the overall observation period will be divided into three mutually exclusive segments:

1. ***pre-treatment period***: from day of patient's informed consent to the day before first administration of eltrombopag
2. ***on-treatment period***: from date of first administration of study treatment to 30 days after date of last administration of eltrombopag.
3. ***post-treatment period***: starting at day 30+1 after last dose of eltrombopag.

Safety summaries (tables, figures) include only data from the on-treatment period with the exception of baseline data which will also be summarized where appropriate (e.g. change from

baseline summaries). In addition, a separate summary for death including on treatment and post treatment deaths will be provided. In particular, summary tables for adverse events (AEs) will summarize only on-treatment events, with a start date during the on-treatment period (**treatment-emergent** AEs).

However, all safety data (including those from the post-treatment period) will be listed and those collected during the pre-treatment and post-treatment period will be flagged.

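### The final SAP's rule for an open dose record uses the end-of-study cut-off as the dose end date, which gives an impossible exposure whenever it applies

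*SAP*

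**What the plan says.** Final-analysis SAP, section 5.1.1, Scenario 1, sets the trigger: "If the dose end date is completely missing and there is no EOT page and no death date, the patient is considered as on-going". The consequence is: "The patient should be treated as on-going and the cut-off date should be used as the dose end date". The rule covers each study treatment component and has no upper limit. The primary-analysis SAP has the same text in its own section 5.1.1.

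Other parts of the plan that bear on it:

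- **Cut-off.** Final SAP 2.1: "The analysis cutoff date for the final analysis of study data will be established at the end of the study". Protocol 9.2 gives two alternative definitions of the end of study. The first is "All participants have died or discontinued from the study or complete the study participation per protocol"; the second is transfer to another study. Follow-up runs to Year 3 (Week 156).
- **Length of treatment.** Protocol 6.1.5: "Eltrombopag will be provided up to Week 52 for the participants who enter the extension part". Final SAP 1.1 agrees: "During the extension part, eltrombopag treatment will be provided up to Week 52". The trial stops supplying CsA after Year 2 (Week 104), and final SAP 2.1.1 limits study treatment to the end of Year 2.
- **Competing statement.** Final SAP 2.1 discusses events without a documented end date and names eltrombopag exposure among them: "For these events, the end date will not be imputed and therefore will not appear in the listings".
- **On-treatment period.** Final SAP 2.1.1: "from date of first administration of study treatment to 30 days after date of last administration of eltrombopag". The same section takes last administration from non-zero doses recorded on the dosage administration record (DAR). It does not say whether an imputed date counts.

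**The concern.** Scenario 1 made sense for the primary analysis. That cut-off came once everyone had reached Week 26 or left, so a responder with an open dose record could well still be on drug. At the end of the study an open record cannot mean that. The final SAP drops or marks as not applicable much that belonged only to the primary analysis (subgroups, primary endpoint, pharmacokinetics), but it keeps this rule as it was.

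What is at stake is the exposure reporting: duration, exposure categories, and dose intensity or cumulative dose. With 36 participants, one wrong record visibly moves a mean. Sections 2.1 and 5.1.1 also point different ways, so two programmers could follow the SAP and produce different tables.

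**Working it through.** **Is anyone still on trial drug at the final cut-off?** Study day = 7 × week + 1 reproduces the days in protocol Table 8-1: Week 26 = 183, Week 52 = 365, Year 2 = 729, Year 3 = 1093.

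Dates given in the documents:
- Last patient first visit: 03-Dec-2021 (protocol, Amendment 3).
- First patient first visit: after 15-Sep-2020 (primary SAP, document history).
- Three participants enrolled by 08-Dec-2020 (protocol, Amendment 2).
- Final SAP: 11-Nov-2024, before the final database lock.

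Assumptions:
- Screening lasts up to 30 days, so the last Day 1 lies between 03-Dec-2021 and 02-Jan-2022, and the first between 16-Sep-2020 and 07-Jan-2021.
- The cut-off date is not stated. I varied it from 11-Nov-2024 (the SAP date) to 28-Jan-2025 (Week 156 plus the 30-day visit window for a Day 1 on 02-Jan-2022).

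On these dates the last possible Week 52 visit, with its 7-day window, is 08-Jan-2023. The last possible Week 104 visit, with its 30-day window, is 30-Jan-2024. On 11-Nov-2024 every participant was at least 149 weeks past Day 1 (1,044 days ÷ 7 = 149.1). Nobody could be on trial-supplied drug.

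**How far off is the imputed date?** Imputed exposure = cut-off − Day 1 + 1 (final SAP 2.4.1). Excess in years = (imputed days − last permitted dosing day) ÷ 365.25. The plan gives no figure of its own to reproduce here.

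| Day 1 | Cut-off | Imputed days | Excess, eltrombopag to Day 365 | Excess, CsA to Day 729 |
|---|---|---|---|---|
| 02-Jan-2022 | 11-Nov-2024 | 1,045 | 1.86 y | 0.87 y |
| 03-Dec-2021 | 28-Jan-2025 | 1,153 | 2.16 y | 1.16 y |
| 07-Jan-2021 | 11-Nov-2024 | 1,405 | 2.85 y | 1.85 y |
| 16-Sep-2020 | 28-Jan-2025 | 1,596 | 3.37 y | 2.37 y |

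For example, (1,045 − 365) ÷ 365.25 = 1.86. If eltrombopag actually stopped at Week 26, the excess is 2.36 years ((1,045 − 183) ÷ 365.25) to 3.87 years ((1,596 − 183) ÷ 365.25).

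**Effect on the summaries.**
- *CsA categories.* The imputed exposure is 1,045 ÷ 30.4375 = 34.3 months to 1,596 ÷ 30.4375 = 52.4 months. The highest category in final SAP 2.4.1 ends at 24 months.
- *Mean eltrombopag exposure.* One affected record among 36 adds (1,093 − 365) ÷ 36 = 20.2 days if the imputed end is Day 1093, or (1,536 − 365) ÷ 36 = 32.5 days if it is Day 1536 (Day 1 on 16-Sep-2020, cut-off 29-Nov-2024).
- *Dose intensity.* Suppose 75 mg/day to Day 365 with the end imputed at Day 1093. If only doses actually taken are summed, dose intensity becomes 75 × 365 ÷ 1,093 = 25.0 mg/day. If the open record is multiplied out, cumulative dose becomes 75 × 1,093 = 81,975 mg instead of 75 × 365 = 27,375 mg. One or the other is wrong.

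**Is the rule meant to be used?** The last contact date paragraph in final SAP 2.1.1 describes this same cut-off imputation of a missing dose end date and bars it from that derivation. That protects overall survival censoring. No similar bar exists for exposure.

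**The case against.** **The trigger may never occur.** All three conditions must hold: no end date, no EOT page and no death date. The protocol requires EOT assessments after any eltrombopag discontinuation (section 3). It also requires discontinuation to be registered in the interactive response system (9.1.1), tracks eltrombopag dispensing there, and queries missing values (11.2). Once an EOT page exists, Scenario 2 applies instead. This stands: few or no records may be affected. It limits how often the rule applies but does not make its answer right.

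**Sections 2.1 and 5.1.1 may serve different purposes.** Section 2.1 can be read as governing display and 5.1.1 as governing derivation; section 5.1.2 makes a similar distinction for adverse events and concomitant medications. That reading is possible, but 2.1 says without qualification that the end date is not imputed, and it names eltrombopag exposure. If 2.1 prevails, no inflated date arises for eltrombopag, but the SAP then gives no end date for calculating exposure.

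**A participant may still be taking CsA.** After Year 2 that is possible through local supply, but final SAP 2.1.1 does not count it as study treatment.

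**Stronger readings.** A reader might infer that the on-treatment period also lengthens by years and that late adverse events and laboratory values flow into the treatment-emergent tables. The documents do not establish this.
- Final SAP 2.1.1 ties last administration to doses recorded on the DAR, so the extension follows only if an imputed date is allowed to count.
- Even then, there would be little to absorb. Adverse event monitoring is required for at least 30 days after the last eltrombopag dose (protocol 10.1.1), and later serious events are reported only if suspected to be related (10.1.3).
- The visit schedule has no adverse event or chemistry collection at Years 2 and 3.
- A participant lost to follow-up contributes no later data.
- The clonal evolution rate is calculated over the whole study in any case.

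A five-day r-ATG course stretched to years is likewise only hypothetical, as the infusions are given in hospital under supervision.

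**Conclusion.** The rule is wrong as written for the final analysis. Whenever it applies, the duration of exposure is impossible and either dose intensity or cumulative dose is wrong with it. The excess is about 1.9 to 3.4 years for eltrombopag taken to Week 52 (longer for earlier stops) and about 0.9 to 2.4 years for CsA taken to Year 2. These ranges rest on the assumed Day 1 and cut-off dates. The finding that nobody is on trial drug holds for any cut-off after 30-Jan-2024.

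The practical consequence is small. The rule acts only on incomplete records, and there may be none. Response rates do not use dose end dates, the primary endpoint is not re-analysed, and survival censoring is protected. Whether the on-treatment period moves is an open question of definition that the SAP should settle.

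**What to change.** In final SAP 5.1.1, delete the cut-off imputation in Scenario 1. Treat such a record as a data issue, a category that section already has, and query it before database lock. If it stays unresolved, use the last dose date supported by DAR or dispensing records. That date should never be later than death, withdrawal of consent, last contact, or the protocol's maximum duration for the component: Week 52 for eltrombopag, end of Year 2 for CsA, last recorded infusion for r-ATG.

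The order matters. Last contact includes survival calls and concomitant medication dates, so a rule built only on last contact and the maximum duration would still carry an early stopper in survival follow-up to Week 52.

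Reconcile section 2.1 with this rule. State in section 2.1.1 that a date imputed from the cut-off does not define last administration.

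The cost is a few sentences in the SAP, a small program change and a listing of open dose records. No new data are needed, and with imputed exposure capped, eltrombopag cannot exceed 365 days (372 with the 7-day visit window) or CsA about 729 days.
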